### Patient treatments and clinical outcomes during CAR-T treatment:

Next step after InO treatment as bridge to CAR-T	Secondary objective: To describe InO treatment patterns in the study population, including chemotherapy regimen and dosage information	eCRF	Next step in treatment	Post InO as bridge to CAR-T
Did the patient receive CAR-T as part of a clinical trial?	Secondary objective: To describe InO treatment patterns in the study population, including chemotherapy regimen and dosage information	eCRF	Clinical trial involvement	Post InO as bridge to CAR-T
Start date of next treatment	Secondary objective: To describe relevant treatment effectiveness outcomes for the study population, including time-to-next treatment and survival To describe InO treatment patterns in the study population, including chemotherapy regimen and dosage information	eCRF	Start date of next treatment	Post InO as bridge to CAR-T
Next treatment ongoing or discontinued	Secondary objective: To describe relevant treatment effectiveness outcomes for the study population, including time-to-next treatment and survival	eCRF	Ongoing/discontinuation of next treatment	Post InO as bridge to CAR-T

R			ct	d
	$\sim$			

Date of discontinuation of next	Secondary objective: To	eCRF	End date of next treatment	Post InO as
treatment	describe relevant treatment			bridge to
treatment	effectiveness outcomes for			CAR-T
	the study population			CAR-1
	including time to next			
	the star and suminal			
D	treatment and survival	CDE	D	D. J.O.
Patients' best response to next	Secondary objective: To	eCRF	Response to next	Post InO as
treatment	describe relevant treatment		treatment	bridge to
	effectiveness outcomes for			CAR-T
	the study population,			
	including time-to-next			
	treatment and survival			
Time from last dose of InO to	Secondary objective: To	eCRF	Time from last InO dose	InO last dose
CAR-T infusion	describe InO treatment		to CAR-T infusion	to CAR-T
	patterns in the study			infusion
	population, including			
	chemotherapy regimen and			
	dosage information			
Number of leukapheresis needed	Secondary objective: To	eCRF	Number of leukapheresis	CAR-T
1	describe InO treatment		required for CAR-T	apheresis
	patterns in the study			"Photosic
	population including			
	chemotherany regimen and			
	dosage information			
Data of laukapharasis	Secondary objective: To	CDE	Data of loukapharagis for	САРТ
Date of leukapheresis	describe InO treatment	eckr	CAP T	CAR-1
	describe mo treatment		CAR-1	apheresis
	patterns in the study			
	population, including			
	chemotherapy regimen and			
	dosage information	~		~
Was leukapheresis successful?	Secondary objective: To	eCRF	Leukapheresis success	CAR-T
	describe InO treatment			apheresis
	patterns in the study			
	population, including			
	chemotherapy regimen and			
	dosage information			
Number of T-cells obtained	Secondary objective: To	eCRF	T-cell number	CAR-T
(CAR-T)	describe InO treatment			apheresis
	patterns in the study			
	population, including			
	chemotherapy regimen and			
	dosage information			
Date of commencement of	Secondary objective: To	eCRF	Date of lymphodepletion	CAR-T
lymphodepletion	describe InO treatment		for CAR-T	received post
	patterns in the study			InO as bridge
	population including			to CAR-T
	chemotherany regimen and			
	dosage information			
Data of initiation of CAP T call	Secondary objective: To	CDE	Data of initiation of	САР Т
infusion	describe InO treatment	CUNF	infusion for CAP T	infusion
	nottoms in the sty 1-		miusion foi CAK-I	musion
	patterns in the study			
	population, including			
	PFIZER CONFIL	DENTIAL		
Redacted				

Page 30 of 55

		1		1
	chemotherapy regimen and			
Number of CAD T - 11		CDE	Number - CADT 11	САРТ
Number of CAR-1 cells	Secondary objective: 10	eckf	Number of CAR-1 cells in	CAR-I
administered in infusion (per kg	describe InO treatment		infusion	infusion
of patient)	patterns in the study			
	population, including			
	chemotherapy regimen and			
	dosage information			
Most recently measured bone	Secondary objective: To	eCRF	Most recent bone marrow	CAR-T
marrow blast count	describe InO treatment		blast count (CAR-T	infusion
	patterns in the study		infusion)	
	population, including			
	chemotherapy regimen and			
	dosage information			
MRD status	Secondary objective: To	eCRF	MRD status at CAR-T	CAR-T
	describe InO treatment		infusion	infusion
	patterns in the study			
	population, including			
	chemotherapy regimen and			
	dosage information			
EMD	Secondary objective: To	eCRF	Presence of EMD at CAR-	CAR-T
	describe InO treatment		Tinfusion	infusion
	patterns in the study			
	population, including			
	chemotherapy regimen and			
	dosage information			
Location of EMD	Secondary objective: To	eCRF	Location of EMD at CAR-	CAR-T
	describe InO treatment	••••	T infusion	infusion
	patterns in the study		1 minubion	musion
	population including			
	chemotherapy regimen and			
	dosage information			
CNS disease	Secondary objective: To	eCRF	Presence of CNS disease	CAR-T
	describe relevant treatment	certi	at CAR-T infusion	infusion
	effectiveness outcomes for			musion
	the study population			
	including time-to-next			
	treatment and survival			
Disease status (salvage 1 etc.)	Secondary objective: To	eCRF	Disease status at CAR-T	CAR-T
Disease status (survage 1 etc.)	describe relevant treatment	con	infusion	infusion
	effectiveness outcomes for		infusion	musion
	the study population			
	including time-to-next			
	treatment and survival			
Type of CAR-T prescribed	Secondary objective: To	eCRF	Type of CAR-T prescribed	CAR-T
Type of CAR-T presended	describe InO treatment	CCRI	Type of CAR-1 presented	received post
	natterns in the study			InO as bridge
	population including			to $CAR_T$
	chemotherany regimen and			10 CAIX-1
	dosage information			
B-cell recovery after CAR-T	Secondary objective: To	eCRF	B-cell recovery post CAR-	CAR-T
influsion	describe relevant treatment	CONT	T infusion	received post
IIIIusioii		I	1 1111031011	received post
Redacted	FFIZER CONFIL	LINIIAL		
Reddeteu				

Page 31 of 55

	effectiveness outcomes for the study population, including time-to-next treatment and survival			InO as bridge to CAR-T
Duration of B-cell recovery (start & end dates captured)	Secondary objective: To describe relevant treatment effectiveness outcomes for the study population, including time-to-next treatment and survival	eCRF	B-cell recovery (duration (start & end date))	CAR-T received post InO as bridge to CAR-T
Patients' response to CAR-T after 1 month	Secondary objective: To describe relevant treatment effectiveness outcomes for the study population, including time-to-next treatment and survival	eCRF	Response to CAR-T (1 month)	CAR-T received post InO as bridge to CAR-T
Patients' response to CAR-T after 3 months	Secondary objective: To describe relevant treatment effectiveness outcomes for the study population, including time-to-next treatment and survival	eCRF	Response to CAR-T (3 months)	CAR-T received post InO as bridge to CAR-T
Patients' response to CAR-T after 6 months	Secondary objective: To describe relevant treatment effectiveness outcomes for the study population, including time-to-next treatment and survival	eCRF	Response to CAR-T (6 months)	CAR-T received post InO as bridge to CAR-T
Patients' response to CAR-T after 12 months	Secondary objective: To describe relevant treatment effectiveness outcomes for the study population, including time-to-next treatment and survival	eCRF	Response to CAR-T (12 months)	CAR-T received post InO as bridge to CAR-T
Most recent bone marrow blast count	Secondary objective: To describe InO treatment patterns in the study population, including chemotherapy regimen and dosage information	eCRF	Most recent bone marrow blast count post CAR-T bridging therapy	Post CAR-T

### Patient treatments and clinical outcomes after CAR-T treatment:

Total number of treatment lines	Secondary objective: To	eCRF	Treatment lines received	Post CAR-T
(ie, number of salvage lines)	describe InO treatment		for ALL post CAR-T	
received for ALL after CAR-T	patterns in the study			
bridging therapy	population, including			
	chemotherapy regimen and			
	dosage information			
	Secondary objective: To			
	describe relevant treatment			

PFIZER CONFIDENTIAL

Redacted

	effectiveness outcomes for			
	the study population			
	including time_to_next			
	treatment and survival			
Treatments or procedures	Secondary objective: To	eCRE	Type of	Post CAR-T
received for ALI	describe InO treatment	CCICI	treatments/procedures	1 Ost CAR-1
Icceived for ALL	notterns in the study		received for ALL post	
	participation including		CAP T	
	abamatharany ragiman and		CAR-1	
	dosage information			
Time to next treatment received	Coordomy abjectives To	CDE		
(start data contured)	describe InO treatment	eckr	treatment received post	FOST CAK-1
(start date captured)	describe into treatment		CAP T	
	patterns in the study		CAR-I	
	abamathanany na siman and			
	de se se information			
Neuchen af UDSCT and a start		CDE	T-t-1 much an a fUDSCT-	
Number of HPSC18 received	Secondary objective: 10	eckr	Total number of HPSC1S	POST CAR-1
	describe into treatment		received	
	patients in the study			
	abamathanany ragiman and			
	desease information			
Deter UDCCT- merilion 1		CDE	Deter UDSCT- we as in a	
Dates HPSC Is received	Secondary objective: 10	ecrf	Dates HPSC Is received	Post CAR-1
	describe ino treatment			
	patterns in the study			
	abamatharany ragiman and			
	dosage information			
Was MPD assagged before this	Secondary objective: To	CDE	MPD assassment corried	
nationt's HDSCT?	describe relevant treatment	CCRI	out before HPSCT	T OST CAR-1
patient s III SC I :	effectiveness outcomes for		out before fill SC I	
	the study population			
	including time-to-next			
	treatment and survival			
Date of the MRD assessment	Secondary objective: To	eCRE	Date of this MRD	Post CAR-T
before this patient's HPSCT	describe relevant treatment	CCRI	assessment	1 OST CAR-1
before uns patient s fil be l	effectiveness outcomes for		assessment	
	the study population			
	including time-to-next			
	treatment and survival			
Method(s) used to assess MRD	Secondary objective: To	eCRF	Methods used to assess	Post CAR-T
before this patient's HPSCT	describe InO treatment		MRD	1 obt office 1
	patterns in the study			
	population, including			
	chemotherapy regimen and			
	dosage information			
	Secondary objective: To			
	describe relevant treatment			
	effectiveness outcomes for			
	the study population,			
	including time-to-next			
	treatment and survival			
	PFIZER CONFID	ENTIAL	·	•

Redacted

Page 33 of 55

Result of the MRD analysis before this patient's HPSCT	Secondary objective: To describe relevant treatment effectiveness outcomes for the study population, including time-to-next treatment and survival	eCRF	Result of MRD analysis	Post CAR-T
Patient's response to HPSCT	Secondary objective: To describe relevant treatment effectiveness outcomes for the study population, including time-to-next treatment and survival	eCRF	Response to SCT	Post CAR-T
Patient diagnosed with GvHD following any of their HPSCT(s)	Secondary objective: To describe relevant treatment effectiveness outcomes for the study population, including time-to-next treatment and survival	eCRF	Presence of GvHD following HPSCT(s)	Post CAR-T
What type of GvHD was the patient diagnosed with following any of their HPSCT(s)	Secondary objective: To describe relevant treatment effectiveness outcomes for the study population, including time-to-next treatment and survival	eCRF	GvHD classification following HPSCT(s)	Post CAR-T

#### 9.4. Data Sources

Data will be collected/extracted from sites based in the UK, US and Spain. The study will involve the abstraction of data from patients' medical charts by healthcare professionals involved in the care of the participants into a secure eCRF. Sites will be asked to provide eCRFs for all patients which they have access to who meet the inclusion criteria. Sites will be instructed to refer to the patients' complete medical record whilst completing the eCRF and not to answer any question from memory or that is not listed within the patients' medical records.

#### 9.5. Study Size

This study is purely descriptive and there will be no limit on the sample size in terms of patients meeting the eligibility criteria. The estimated number of patients based on the feasibility study is expected to be n = 79.

#### 9.6. Data Management

#### 9.6.1. Case Report Forms (CRF)/Data Collection Tools (DCTs) /Electronic Data Record

As used in this protocol, the term CRF should be understood to refer to either a paper form or an electronic data record or both, depending on the data collection method used in this study.

A CRF is required and should be completed for each included patient. The completed original CRFs are the sole property of Pfizer and should not be made available in any form to third parties, except for authorised representatives of Pfizer or appropriate regulatory authorities, without written permission from Pfizer. The investigator shall ensure that the CRFs are securely stored at the study site in encrypted electronic and/or paper form and will be password protected or secured in a locked room to prevent access by unauthorised third parties.

The investigator has ultimate responsibility for the collection and reporting of all clinical, safety, and laboratory data entered on the CRFs and any other data collection forms (source documents) and ensuring that they are accurate, authentic/original, attributable, complete, consistent, legible, timely (contemporaneous), enduring, and available when required. The CRFs must be signed by the investigator or by an authorised staff member to attest that the data contained on the CRFs are true. Any corrections to entries made in the CRFs or source documents must be dated, initialled, and explained (if necessary) and should not obscure the original entry.

The source documents are the hospital or the physician's chart. In these cases, data collected on the CRFs must match those charts.

#### 9.6.2. Record Retention

To enable evaluations and/or inspections/audits from regulatory authorities or Pfizer, the investigator agrees to keep records, including the identity of all participating patients (sufficient information to link records, eg, CRFs and hospital records), copies of all CRFs, safety reporting forms, source documents, detailed records of treatment disposition, and adequate documentation of relevant correspondence (eg, letters, meeting minutes, and telephone call reports). The records should be retained by the investigator according to local regulations or as specified in the clinical study agreement (CSA), whichever is longer. The investigator must ensure that the records continue to be stored securely for so long as they are retained.

If the investigator becomes unable for any reason to continue to retain study records for the required period (eg, retirement, relocation), Pfizer should be prospectively notified. The study records must be transferred to a designee acceptable to Pfizer, such as another investigator, another institution, or to an independent third party arranged by Pfizer.

Study records must be kept for a minimum of 15 years after completion or discontinuation of the study, unless Adelphi Real World and Pfizer have expressly agreed to a different period of retention via a separate written agreement. Record must be retained for longer than 15 years or as required by applicable local regulations.

The investigator must obtain Pfizer's written permission before disposing of any records, even if retention requirements have been met.

#### 9.7. Data Analysis

The study is not intended to test hypotheses and is primarily descriptive in nature, therefore descriptive analysis will be conducted to meet the majority of the pre-specified objectives. Frequencies and percentages will be reported for categorical variables, including the percentage of missing/unknown data, while counts, number of missing, means, medians, standard deviations (SDs), first and third quartiles, minimum and maximum values will be reported for continuous numeric variables. Where applicable, all estimates will be described with accompanying 95% confidence intervals (CI). Outcomes such as OS will be assessed via time to event analyses, with KM curves and 95% CI estimated for KM curves outputted. This will be calculated using variables in the CRF. For example, OS will be calculated from the first dose of InO to point of death. Censoring will be applied if the patient is alive at the point of data capture.

Data analysis will be aligned with data extracted/collected from all data sets. Where specific variables or outcomes cannot be assessed/described subgroup analyses could be conducted for a subset of patients from certain data sources.

All analyses will be conducted using Stata 17 software, version 17 or the latest available version (StataCorp, College Station, Texas).

Detailed methodology for summary and statistical analyses of data collected in this study will be documented in a statistical analysis plan (SAP), which will be dated, filed, and maintained

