#### 6. MILESTONES

Milestone	Planned date
Registration in the Heads of Medicines (HMA)- European Medicines Agency (EMA) Catalogues of RWD studies	16 April 2024
Start of data collection	16 December 2024
End of data collection	16 June 2025
Final study report	31 August 2025

The data collection period is expected to be from December 2024 to June 2025 and will only include data collected in a retrospective manner. Only data available within the patients' medical record at the point of data entry will be eligible for inclusion in the eCRF; no prospective data entry is included in the study design.

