#### 9.2.1. Inclusion Criteria

Patients must meet all of the following inclusion criteria to be eligible for inclusion in the study:

1. Patient has a clinical diagnosis of R/R PBC ALL

PFIZER CONFIDENTIAL

Redacted

- 2. Patient is aged 18 years or older at start of InO therapy
- 3. Patient received InO treatment as a bridge to CD19-directed CAR-T cell therapy (is defined as either patient received InO immediately prior to apheresis, and/or patient received InO after apheresis and before CAR-T cell infusion. In either case, InO was used with the aim of preventing uncontrolled disease progression and facilitating successful progression to CAR-T cell therapy. Such patients are eligible to be included even if CAR-T was not ultimately administered from index date (01 June 2017)
- 4. Patients with data points available for a minimum of 3 months data from the first dose of InO are eligible for inclusion within the study. Permitted exceptions to the minimum 3-month follow-up requirement include:
  - a. Patients who die within the 3 months
  - b. Patients who proceed to a CD19 CAR-T clinical trial within the 3 months

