#### Screener:

Variable	Role	Data source(s)	Operational definition	Time-point
Has this patient been diagnosed with R/R B-cell leukaemia ALL?	To determine eligibility for study	eCRF	R/R (PBC) ALL diagnosis	R/R (PBC) ALL diagnosis
Patient's age (or one categorical response if aged $\ge 90$ )	To determine eligibility for study	eCRF	Patients age at InO 1 st dose	1 st dose of InO (index)
Did the patient initiate InO treatment 01 June 2017 onwards as a bridging therapy to intended CAR-T?	To determine eligibility for study	eCRF	InO initiation as bridge to CAR-T date	1 st dose of InO (index)
Is the patient currently alive?	To determine eligibility for study	eCRF	Patient's vital status	Anytime up to/including data collection

Variable	Role	Data source(s)	Operational definition	Time-point
Does the patient have at least 3 months' follow up data from the first dose of InO to the date of last assessment? Note: Patients who die within the 3 months or proceed to a CD19 CART clinical trial are eligible for inclusion within the study	To determine eligibility for study	eCRF	Follow up status	1 st dose of InO (index) to date of last assessment
Has the patient received at least one dose of InO bridging to CAR-T therapy and then completed CAR- T therapy (if they could receive it)?	To determine eligibility for study	eCRF	InO bridging therapy status	Anytime up to/including data collection

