### Patient demographics:

Variable	Role	Data source(s)	Operational definition	Time-point
Patient's biological sex	Primary objective	eCRF	Patient's biological sex	N/A
Patient's race/ethnicity	Primary objective	eCRF	Patient's race/ethnicity	N/A
Patient Hispanic/Latin/Spanis h origin	Primary objective	eCRF	Origin	N/A
Patient's BMI	Primary objective	eCRF	Patient's BMI at index	1 st dose of InO (index)
Date of patient's death (if applicable)	Primary objective	eCRF	Time since death	Anytime up to/including data collection
Primary cause of patient's death (if applicable)	Primary objective	eCRF	Primary cause of death	Anytime up to/including data collection
Is the patient actively being monitored or have they been lost to follow up?	Primary objective	eCRF	Patient lost to follow up	Anytime up to/including data collection
Last date of activity for this patient (if lost to follow up)	Primary objective	eCRF	Time since last date of activity/ time since lost to follow up	Anytime up to/including data collection

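### The OS censoring rule names no censoring date, and a last date of activity is listed only for patients flagged as lost to follow-up

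*Protocol*

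**What the plan says.** Protocol section 9.7 gives OS as its example of a time-to-event outcome: "OS will be calculated from the first dose of InO to point of death". The next sentence is the only censoring rule in the document: "Censoring will be applied if the patient is alive at the point of data capture". It gives no censoring date and no rule for a patient whose status at capture is unknown. The same section says that these outcomes are computed from CRF variables and leaves detailed methods to a SAP.

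Section 9.3 lists the relevant fields:

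- Screener: "Is the patient currently alive".
- Patient demographics: date of death where applicable, then "Is the patient actively being monitored or have they been lost to follow up", and then the conditional field "Last date of activity for this patient (if lost to follow up".
- A date of last assessment appears only inside the eligibility question on 3 months of "follow up data from the first dose of InO to the date of last assessment". It is not a variable of its own.

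Section 6 confines the study to what the medical record holds at data entry: only such data "will be eligible for inclusion in the eCRF; no prospective data entry is included in the study design". No death-registry linkage is described.

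Two groups may leave the site's view without being called lost. Section 9.2.1 exempts from the follow-up minimum "Patients who proceed to a CD19 CAR-T clinical trial within the 3 months". Section 9.9 expects an embargo on data from CAR-T infusion onwards for up to about 50% of Spanish patients.

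**The concern.** A chart shows that a patient was alive at the last documented contact, not on the day someone fills in the form. Index dates run from June 2017, and capture was planned for December 2024 to June 2025, so the two dates can be far apart. A rule that mentions only the point of data capture invites an analyst to use that date for every patient without a recorded death. Any death after the last contact that never reached the chart then becomes event-free follow-up, and the tail of the Kaplan-Meier curve is too high.

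This is not only a matter for the SAP. A SAP can define the censoring date, but it cannot recover a date that was never collected. Section 9.8 locks each eCRF after review, and this protocol version is dated 09 May 2025, against a planned end of data collection on 16 June 2025.

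**Working it through.** **Step 1. Who has a usable date, as section 9.3 stands.**

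- Died: date of death.
- Alive or unknown, flagged as lost: last date of activity.
- Alive, actively monitored: no last-known-alive date listed.
- Moved to a CD19 CAR-T trial, or embargoed: a date only if the site flags the patient as lost. A patient followed within a trial may well be recorded as monitored.

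The gap therefore lies in the last two groups.

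**Step 2. No figure in the plan to reproduce.** The protocol gives no expected OS and no loss rate. The 79 patients in section 9.5 are a feasibility count. The sizes below rest on assumptions.

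**Step 3. Patients who go unobserved and are censored at capture.** Assume exponential OS with hazard λ = ln 2 / median. Assume that a share p of patients has a loss time L uniform over 0 to 24 months, independent of prognosis, and that no death is recorded after L. Capture-date censoring then adds to true survival the probability of a hidden death by time t. For t of 24 months or more:

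bias(t) = p × P(L < T ≤ t) = p × [(1 − e^(−24λ)) / (24λ) − e^(−λt)]

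For a median of 12 months, 24λ = 1.386 and e^(−24λ) = 0.25. The bracket at 24 months is 0.75 / 1.386 − 0.25 = 0.291. Multiplying by p = 0.05, 0.10 and 0.20 gives 1.5, 2.9 and 5.8 points.

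For a median of 6 months the bracket is 0.9375 / 2.773 − 0.0625 = 0.276. For a median of 24 months it is 0.5 / 0.693 − 0.5 = 0.221.

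A Kaplan-Meier simulation (200,000 patients per scenario) used entry from June 2017 to 3 months before capture began and capture from mid-December 2024 to mid-June 2025. It gave these rises in 24-month OS, in percentage points:

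| Assumed median OS | p = 5% | p = 10% | p = 20% |
|---|---|---|---|
| 6 months | 1.4 | 2.8 | 5.7 |
| 12 months | 1.5 | 2.9 | 6.0 |
| 24 months | 1.2 | 2.3 | 4.6 |

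The simulation sits slightly above the formula because it draws loss times over a shorter window for patients with less than 24 months of possible follow-up. With a median of 12 months, 24-month OS reads 26.6%, 28.0% and 30.9% instead of 25%, and the median reads 12.3, 12.4 and 13.0 months instead of 12.0. At 36 months with p = 20%, the rises are 6.6, 8.4 and 7.5 points for medians of 6, 12 and 24 months. With p = 0 the two rules agree exactly. Loss earlier than the uniform pattern, such as at infusion, would give more for the same p.

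**Step 4. How p relates to the embargo.** Spain's share of the cohort is not stated. At the 50% limit, embargoed patients are 0.5 × Spain's share, so p = 5% and p = 20% correspond to Spanish shares of 10% and 40%.

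**Step 5. Patients still monitored.** Assume a last visit uniform over the 3 or 6 months before capture, with half of the deaths in that gap unrecorded. With a 6-month gap, simulated 24-month OS under capture-date censoring is 6.7%, 25.4% and 50.8%, against true values of 6.25%, 25% and 50%. The rises are 0.4 to 0.8 points. With a 3-month gap they are smaller.

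**Step 6. Scale.** With 79 patients, no censoring and survival of 50%, the 95% CI half-width is 1.96 × √(0.25 / 79) = 0.110, or about 11 points.

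**The case against.** A reader might infer that the protocol itself credits lost patients with survival up to data capture, and so builds an upward bias into OS. The documents do not support this. The sentence in section 9.7 says who is censored, not when. A lost patient is not known to be alive at capture, so the sentence does not cover that patient. For patients flagged as lost, section 9.3 collects the date that correct censoring needs.

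For the same reason, a large bias derived from ordinary loss to follow-up would be charged to the wrong group. It describes the patients who do have a last date of activity. For the rest, it is also too strong to say that form completion is the only possible censoring date. Sites must look up the date of last assessment to answer the eligibility question. Other dated events (next treatment, MRD, transplant) are collected. Section 9.3 says that the variables become final only with the CRF. If a site truly confirms vital status on the day of capture, that day is a valid censoring date.

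It is also fair to say that exact censoring dates are routine SAP content, that OS is introduced only as an example, and that section 9.9 already warns that OS may not be assessable for many patients.

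What stands is narrower. The rule names no date. The one suitable field is conditional on a flag that monitored, trial and embargoed patients may not carry. Dates of treatment events are not dates last known alive. A SAP cannot make up for a field left blank on a locked form.

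**Conclusion.** The point holds as a gap in the rule and the field list, not as a bias that the protocol has fixed. OS would be biased upward only if the capture date were used for patients not observed up to it.

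Under the stated assumptions, the bias is zero with complete follow-up. It is about 1 point or less for monitored patients last seen within 3 to 6 months of capture. It is about 1 to 6 points at 24 months if 5 to 20% of patients went unobserved during the first 24 months and were censored at capture. The loss rates, the timing of loss and the share of unrecorded deaths are all assumed. The largest of the 24-month figures is about half of the 11-point CI half-width, but it is systematic and always flatters OS.

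Severity is moderate: OS is a secondary, descriptive outcome with no comparison. The change is worth making because it is cheap and depends on data collected before forms are locked.

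**What to change.** In section 9.7, state that patients without a recorded death are censored at the last date documented alive in the chart, and that for embargoed patients this is the last date with accessible data. State that the eCRF completion date is not used as the censoring date.

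In section 9.3, remove the loss-to-follow-up condition from the last date of activity, so that the date is collected for every patient without a recorded death. First check the live eCRF and the SAP, either of which may already do this.

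The cost is one sentence and one branch on an existing field. Follow-up becomes slightly shorter and the OS tail slightly less favourable. Some locked eCRFs may need to be re-opened to add the date.
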